3. STUDY DESIGN

3.1. Study Overview

This is a Phase 1, open-label, multi-center, multiple-dose, dose escalation and expansion, safety, PK, and pharmacodynamic study of PF-06801591 in previously treated patients with locally advanced or metastatic solid tumor types with clinical evidence of response to anti PD-1 or PD-L1 agents. This clinical trial will include 2 parts: Part 1 dose escalation, and Part 2 dose expansion (see Figure 4). A total of approximately 140 patients will be enrolled into this study.

Figure 4. B8011001 Study Schematic

Part 1 will enroll patients with locally advanced or metastatic melanoma, SCCHN, ovarian cancer, sarcoma, NSCLC, urothelial carcinoma, or other solid tumor types with clinical evidence of response to anti PD-1 or PD-L1 agents. Patients will receive 0.5, 1, 3, or 10 mg/kg PF-06801591 intravenously (IV) every 3 weeks (q3w), or 300 mg PF-06801591 subcutaneously (SC) every 4 weeks (q4w).

Part 1 will be further divided into Part 1A (safety cohort) and Part 1B (pharmacodynamic cohort). For both IV and SC administration portions, each safety cohort will enroll 2-4 patients per dose level. For IV administration portion, each pharmacodynamic cohort will enroll 2 to 5 patients per dose level. For SC administration portion, up to approximately 11 patients will be enrolled into the 300 mg dose level in Part 1B. Approximately 40 patients will be enrolled into Part 1.

All patients in Part 2 will receive 300 mg PF-06801591 subcutaneously q4w. Part 2 dose expansion will include 2 arms: Arm 1 will enroll approximately 70 patients with NSCLC who progressed on or were intolerant to systemic therapy or for whom systemic therapy was refused or unavailable but have not previously received anti-PD-1 or anti-PD-L1. Arm 2 will enroll approximately 30 patients with urothelial cancer who progressed on or were intolerant to systemic therapy or for whom systemic therapy was refused or unavailable but have not previously received anti-PD-1 or anti-PD-L1. Approximately 100 patients will be enrolled into Part 2.

All patients:

1. Will undergo up to 4 weeks of screening prior to study entry.
2. Receive treatment with investigational product for up to 2 years, or until one of the following:
 - a. Disease progression by immune-related Response Evaluation Criteria in Solid Tumors (irRECIST, confirmed progressive disease [PD] or initial PD followed by rapid clinical deterioration), or
 - b. Unacceptable toxicity occurs, or

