Confirmation of response (complete response [CR]/partial response [PR]) with a second consecutive scan at least 4 weeks later is preferred. Tumor assessments should be repeated at the End of Treatment visit if more than 6 weeks (IV) or 8 weeks (SC) have passed since the last evaluation. CT or MRI scans should be completed before tumor biopsy samples are collected. If a patient is classified as having progressive disease (PD) at a post-baseline tumor assessment, then confirmation of PD by a second consecutive scan at least 4 weeks later in the absence of rapid clinical deterioration is required. After End of Treatment for patients who did not end treatment due to disease progression, death, or withdrawal of consent, a tumor assessment will be performed every 12 weeks (± 1 week), until disease progression by irRECIST, or initiation of a new anti-cancer treatment, or end of trial (2 years after LPFD, see [Section 13.2](#)), whichever is first.

If imaging is used in disease assessment, the same imaging technique used to characterize each identified and reported lesion at baseline will be employed in post-baseline disease assessments whenever possible.

Disease response assessments will be based upon disease-specific response criteria: RECIST v 1.1 ([Appendix 3](#)) and irRECIST ([Appendix 4](#)).

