- Overall immune-related partial response (irPR): Sum of the diameters (longest for non-nodal lesions, shortest for nodal lesions) of target and new measurable lesions decreases $\geq 30\%$.

- Overall immune related stable disease (irSD): Sum of the diameters (longest for non-nodal lesions, shortest for nodal lesions) of target and new measurable lesions is neither irCR, irPR, (compared to baseline) nor immune related progressive disease (irPD, compared to nadir).
- Overall irPD: Sum of the diameters (longest for non-nodal lesions, shortest for nodal lesions) of target and new measurable lesions increases $\geq 20\%$ (compared to nadir) with a minimum absolute increase of 5 mm, confirmed by a repeat, consecutive observation at least 4 weeks from the date first documented.

New measurable lesions: Incorporated into tumor burden (ie, added to the target lesion measurements). A lymph node has to be ≥ 15 mm in short axis to be a measurable new lesion and its short axis measurement is included in the sum. Up to 2 new lesions per organ and up to 5 new lesions in total can be added to the measurements at each assessment time point.

New non measurable lesions: Do not define progression but preclude irCR.

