3.2. Secondary Endpoint(s)

Part 1:

- PK parameters of PF-06801591: Cycle 1 and Cycle 4 C_{max} , area under the concentration versus time curve (AUC) from time zero to the last quantifiable time point prior to the next dose (AUC_{last}), and if data permit, CL, V_d , volume of distribution at steady state (V_{ss}), accumulation ratio (Rac) when feasible, and terminal elimination $t_{1/2}$.
- Incidence of anti-drug antibodies (ADA) and neutralizing antibodies (NAb) against PF-06801591.
- PD-1 receptor occupancy (RO) by PF-06801591, as assessed by measuring the levels of unbound (free) cell surface PD-1 on circulating T cells over time following PF-06801591 administration.
- Objective tumor response, as assessed using the Response Evaluation Criteria in Solid Tumor (RECIST) version 1.1 and immune-related RECIST (irRECIST); and proportion of subjects with PR (and irPR, as appropriate).
- Time-to-event endpoints based on RECIST and irRECIST and PFS (and irPFS as appropriate), Duration of stable disease (DOSD, or irDOSD as appropriate), and Duration of response (DOR, or irDOR as appropriate).
 - PFS is defined as the time from treatment start date to date of first documentation of progression or death due to any cause.
 - Duration of stable disease is defined from the start of the treatment until the criteria for progression are met, taking as reference the smallest tumor measurements recorded since the treatment started, including the baseline measurements. This endpoint is applicable to the subset of patients who achieved a best overall response of stable disease (SD), those patients whose best overall response is not SD will be excluded from this endpoint analysis. A minimum of 6 weeks (with a - 5 days window, which is essentially a minimum of 35 days) interval of two assessments is required for this endpoint.
 - Duration of response is defined as the time from start date (which is the date of first documentation of PR or CR) to date of first documentation of objective progression or death. DOR is only applicable to those patients with an objective response.

Part 2:

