6. ANALYSES AND SUMMARIES

For efficacy related endpoints in this study, as both RECIST 1.1 and irRECIST will be used for tumor assessments, and there are different requirements in these criteria in terms of confirming tumor response or progression, the following analysis plan will be implemented:

Endpoint	Part 1		Part 2	
	RECIST 1.1	irRECIST	RECIST 1.1	irRECIST
ORR (or irORR)	Unconfirmed	Both	Both	Both
PFS (or irPFS)	Unconfirmed	Both	Unconfirmed*	Both
DOR (or irDOR)	Unconfirmed	Both	Both	Both
DOSD (or irDOSD)	Unconfirmed	Both	Both	Both
TTP	Unconfirmed	Both	Unconfirmed*	Both
TTR	Unconfirmed	Both	Both	Both

Note: “Both” in the above table represents both unconfirmed and confirmed tumor assessments.

*: Confirmation for progressed disease is not applicable in RECIST 1.1

In the “unconfirmed” analyses (i.e. tumor response or progression without confirmation required), all tumor assessments data will be included for analyses. Specifically, regardless if a patient’s tumor response or progression is subsequently confirmed or not, the patient data will all be included in the “unconfirmed” analyses. This is a more comprehensive analysis where tumor confirmation is not required and not taken into account. For example in the ORR analysis, if a patient achieved CR or PR, regardless it is subsequently confirmed or not, the patient will be included in the numerator.

In the “confirmed” analyses (i.e. tumor response or progression with confirmation required), only those tumor assessments data that’s subsequently confirmed by a consecutive tumor scan will be considered as a “success” or “event” and be included for analyses as appropriate. For example, in the ORR analysis, a patient will only be counted in the numerator (the “success”) if the tumor response (CR or PR) is subsequently confirmed. If a patient’s tumor response is not subsequently confirmed, the patient will still be included in the denominator (the population set) but will not be included in the numerator (the “success”). In the PFS analysis, only a PD that’s subsequently confirmed will be considered as an “event”.

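### In the confirmed irRECIST analyses, initial PD with rapid clinical deterioration and no second scan is not an event: confirmed irTTP is biased upward, and confirmed irPFS is dated late or censored

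*SAP*

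**What the plan says.** **The analysis rule.** SAP Section 6 plans unconfirmed and confirmed versions of irPFS, irDOR, irDOSD, TTP and TTR under irRECIST in both parts: the table entry Both "in the above table represents both unconfirmed and confirmed tumor assessments". In the confirmed version, only assessments "subsequently confirmed by a consecutive tumor scan will be considered as a" success or event. For PFS, only a PD that is "subsequently confirmed will be considered as an" event. No exception is given.

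**The protocol's treatment and scanning rules.** Protocol Section 3.1 (and the Protocol Summary) explains progression by irRECIST, as a reason to stop treatment, as "confirmed progressive disease [PD] or initial PD followed by rapid clinical deterioration". Section 7.4 says that after a first PD "confirmation of PD by a second consecutive scan at least 4 weeks later in the absence of rapid clinical deterioration is required". Once dosing has stopped, scanning is limited to "patients who did not end treatment due to disease progression, death, or withdrawal of consent, a tumor assessment will be performed every 12 weeks".

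**The protocol's response definition.** Appendix 4 defines irPD as an increase "confirmed by a repeat, consecutive observation at least 4 weeks from the date first documented". Appendix 5, Table 9, footnote b also demands confirmation. Neither mentions deterioration, and SAP Appendix 9.5 repeats the Appendix 4 definition.

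**Deaths and censoring.** SAP Section 3.2 states: "PFS is defined as the time from treatment start date to date of first documentation of progression or death due to any cause". SAP Table 9.2.1 makes death an event for PFS unless it follows two or more missed assessments, when the patient is censored at the last assessment before it. SAP Table 9.2.2 censors death without objective progression at the last assessment before death.

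**The concern.** The SAP asks for a second scan in exactly the patients for whom the protocol waives it. Once such a patient stops for progression, no further scan is scheduled, so the confirming scan will usually not exist. No row of Tables 9.2.1 or 9.2.2 is written for this case.

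The reason for the missing confirmation is the course of the disease. Treating these patients as censored assumes that they carry the same later risk as those still under observation, which cannot be right when they left because they were declining. The confirmed analysis is meant to set aside flare-type increases that later recede. As worded, it also sets aside progressions on which the protocol stops treatment. Protocol Section 1.2.7 intends Part 2 to be read against approved intravenous anti-PD-1 agents, so an upward-biased time-to-event estimate can mislead even without a test.

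**Working it through.** The documents state no event count, power or precision figure for these endpoints, so there is no planned figure to reproduce. The check traces one patient through the rules and then illustrates size under stated assumptions.

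**1. Patient trace.** First irPD on a scheduled scan, rapid deterioration, treatment stopped, no later scan.

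| Analysis | Outcome under the SAP as written |
|---|---|
| Unconfirmed irPFS and irTTP | Event at the first PD scan |
| Confirmed irTTP | Never an event; censored at the last assessment, normally the PD scan itself, whether or not the patient dies |
| Confirmed irPFS, death before two missed assessments | Event, at the later death date |
| Confirmed irPFS, death after two or more missed assessments, or alive | Censored at the last assessment |

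The SAP does not say whether scans no longer scheduled after end of treatment count as missed. If they do not, more deaths stay in irPFS as events, again at later dates.

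**2. Confirmed irTTP, illustration.** From the documents: scans every 8 weeks on the SC schedule (Protocol Section 7.4). Assumed: exponential time to progression with median 16 weeks; a fraction q of progressors deteriorate rapidly and have no second scan, with q from 10% to 30%; all other PDs are confirmed and dated at the first PD scan.

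- Probability of progression per 8-week interval: 1 − 2^(−8/16) = 0.2929.
- All first PDs counted, week 24 (three scans): (1 − 0.2929)³ = 0.354.
- Fraction q censored at the PD scan: (1 − 0.2929(1 − q))³.
  - q = 10%: (1 − 0.2636)³ = 0.399
  - q = 20%: (1 − 0.2343)³ = 0.449
  - q = 30%: (1 − 0.2050)³ = 0.502

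A simulation of 200,000 patients under these assumptions gives the same values to within 0.002.

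**3. Confirmed irPFS: who stays an event.** Take two missed 8-week scans as 16 weeks, count unscheduled scans as missed, and assume exponential survival after PD with median m weeks. The share of affected patients kept as death events is 1 − 2^(−16/m):

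| m (weeks) | 4 | 8 | 16 | 26 |
|---|---|---|---|---|
| Kept as events | 94% | 75% | 50% | 35% |

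Those who die fastest are mostly kept, at a later date. Those who live longer are mostly censored.

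**4. Confirmed irPFS, illustration.** The same simulation, with deaths handled as in step 3, gives these week-24 estimates against 0.35 when all first PDs count:

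| q | Week-24 estimate, m from 4 to 26 weeks |
|---|---|
| 10% | 0.37 to 0.39 |
| 20% | 0.40 to 0.43 |
| 30% | 0.42 to 0.47 |

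The direction is the same as for irTTP and the shift is smaller.

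**The case against.** - **The SAP follows the protocol's own irPD definition.** This stands. Appendices 4 and 5 require confirmation without exception; the waiver appears only in the treatment and scanning rules. A reader might infer that the SAP simply departs from the protocol. The documents do not support that: the protocol disagrees with itself and the SAP follows one side. The gap in the analysis remains.
- **The fastest progressors are not simply censored.** This stands for irPFS. It is tempting to say that the sickest patients drop out of both endpoints, but death is a PFS event, so most early deaths stay in. The sentence in SAP Section 6 separates confirmed from unconfirmed PD and does not say that deaths are dropped. For irTTP the censoring is as described.
- **The unconfirmed analyses already count these patients.** True, so the information is not lost. But those analyses also count flare-type increases that are never confirmed. Neither version matches the protocol's description of irRECIST progression in Section 3.1.
- **A later scan may exist.** Section 7.4 asks for a scan at withdrawal if none was done in the previous 3 weeks, and Appendix 3 asks for every effort to document progression after discontinuation. A scan at least 4 weeks after the first PD would confirm some cases, which lowers q without closing the gap.
- **The endpoints are minor.** They are secondary, the irRECIST versions are to be explored when appropriate and data permit (SAP Section 5.3.1), and there is no hypothesis test (SAP Sections 5.1 and 5.2.3). That limits the consequence. No sample size or error rate changes.

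**Conclusion.** The point holds in limited form. For confirmed irTTP, the stated rules censor initial PD with rapid deterioration and no second scan at about the PD scan, and the bias is upward. For confirmed irPFS the effect is mixed: later event dates for early deaths, and censoring for those who survive or die after two or more missed assessments. Progression in confirmed irDOR and irDOSD has the same gap.

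The size is unknown. The week-24 figures rest on an assumed 16-week median, an assumed 10% to 30% of progressors affected and, for irPFS, an assumed 4 to 26 weeks' median survival after PD; none of these is in the documents. A count of lost events would be equally assumed. A reader might infer that the trial's efficacy conclusion is at risk. The documents do not support that: Part 2's primary efficacy endpoint is ORR, and the unconfirmed analyses are reported alongside. The rule is still worth correcting, because its bias has a known direction and the correction is cheap.

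**What to change.** Add a rule to SAP Section 6, with matching rows in Appendix 9.2, before the database is released. In confirmed irPFS and irTTP, and for progression in confirmed irDOR and irDOSD, count an event dated at the initial PD when either:

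1. the PD is confirmed by a scan at least 4 weeks later; or
2. there is no later scan, and the initial PD is followed by treatment discontinuation for progression or global deterioration of health status, or by death.

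State that other deaths remain events in confirmed irPFS, and whether scans not scheduled after end of treatment count as missed. Name the CRF fields that identify these patients. The discontinuation reason (Protocol Section 6.6) and the death date (listed in SAP Section 6.3.1) should serve, but no field for rapid clinical deterioration is described and the term is not defined. Reconcile Protocol Sections 3.1 and 7.4 with Appendices 4 and 5 and SAP Appendix 9.5.

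The cost is a short paragraph, some programming and a check of the CRF fields. The downside is small: a few unconfirmed PDs enter the confirmed analysis on the strength of the discontinuation reason. Reporting their number would let readers judge the effect.

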6.1. Standard Analyses

Study Conduct and Patient Disposition

An accounting of the study patients will be tabulated. The subject evaluation groups will be listed. The Full Analysis Set will be used.

Subject discontinuation from treatment and study will be tabulated and listed separately with their reason for discontinuation. The Safety Analysis Set will be used.

Baseline Characteristics

Baseline characteristics such as demographics, prior medication, medical history, ECOG performance status, and primary diagnosis will be tabulated and listed. For ECOG performance status a shift table (worst post-baseline vs baseline may be produced). The Safety Analysis Set will be used.

Treatment Administration/Compliance

Listings and tables by dose level will be provided. Cycle length is 21 days (+/- 2 days) for IV infusion and 28 days (+/- 2 days) for subcutaneous administration. Day 1 of a cycle is the first date of dose within that cycle. The safety analysis set will be used.

Dose modifications may occur in the following ways:

- Cycle delay—Day 1 of current cycle starts later than 21 (+2) days from Day 1 of the previous cycle (only applies to cycle 2 and above). For subcutaneous administration, 28 (+2) days, rather than 21 (+2) days, will be used in determining cycle delay. For example, after cycle 1 ended for a patient in Part 2, a new cycle didn't start until 28 (+2) days after (but before 56 days after) cycle 1 day 1, the newly started cycle will be considered as cycle 2, and cycle 2 is considered delayed.
- Cycle skip – Day 1 of current cycle starts later than 42 (+4) days from Day 1 of the previous cycle (only applies to cycle 2 and above). For subcutaneous administration, 56 (+4) days, rather than 42 (+4) days, will be used in determining cycle skip. For example, After cycle 1 ended for a patient in Part 2, a new cycle didn't start until 56 (+4) days after cycle 1 day 1, the newly started cycle will be considered as cycle 3, and cycle 2 is considered skipped for this patient.
- Dose reduction— a decrease in the administered total daily dose (non-zero) compared to the planned total daily dose upon enrollment. If in the CRF the prescribed dose unit is mg/kg, but the actual dose is in mg the actual dose mg/kg should be calculated considering the body weight of the patient at that visit. Inpatient dose reductions are not permitted during the study unless, in discussion with the sponsor, a dose level is deemed beyond the determined MTD.

The following will be summarized by subject for overall and each dose level:

- Number of subjects per dose level;
- Median and range of number of cycles started per subject;
- Number (%) of subjects starting a cycle (1, 2, 3...);
- Number (%) of subjects with cycle delays and cycle skips;
- Number (%) of dose interruptions (include both known and unknown dates);
- Number (%) of subjects with dose reductions;
- Number (%) of each reason (drug related AE vs AE vs. Other) for cycle delays, dose interruptions and dose reductions;

- Time on treatment (median, range).

The following will be summarized by cycle received for overall and each dose level:

- Total number of cycles started;
- Number of cycles started per subject (median, range);
- Number of cycles before 1st delay (median, range);
- Number of cycles before 1st reduction (median, range);
- Number of cycles before 1st interruption (median, range);
- Number of cycles before 1st dose skip (median, range).

The following will be summarized for cumulative dose by dose level and cycle:

- Summary statistics (mean, median, standard deviation and range) of cumulative dose and percent of starting dose (compared to Day 1 dose of each cycle).

Listings by subject (ordered by dose level): start date and stop date of each dosing period within each cycle (including records with 0 mg), administered total daily dose for each period, any missed doses with unknown dates (Y/N), number of missed doses with unknown dates, reason for any dosing changes.

Listings by subject and each cycle (ordered by dose level): cycle length, total planned dose, administered total dose, percentage of planned dose, dose delay (yes/no), dose reduction (yes/no), and dose interruption (yes/no).

Prior, Concomitant, and Further Therapies

Prior, concomitant, and further therapies (drug and non-drug treatments) will be coded by the World Health Organization (WHO) medical dictionary. Listings of prior, concomitant, and further therapies will be provided separately.

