5.4. Administration

5.4.1. IV Administration (Part 1 Only)

PF-06801591 will be administered intravenously, with adjustment for body weight at every cycle. Patient actual body weight will be used to calculate the mg/kg dose, and the calculated dose will be rounded off to the second decimal point. In each cycle, patients should be weighed within 72 hours prior to dosing to ensure they did not experience weight loss/gain of >10% from the prior weight used for PF-06801591 dose preparation calculations.

The decision to recalculate PF-06801591 dose based on the weight obtained at each cycle may be in accordance with institutional practice; however if the patient experienced either a weight loss or gain of >10% compared to the weight used to calculate the most recent dose, the amount of PF-06801591 required for study drug preparation and administration for the current cycle must be recalculated using this most recent weight obtained.

PF-06801591 will be administered on an outpatient basis as an IV infusion on Day 1 of each 21-day treatment cycle, initially over 60 minutes \pm 10 minutes. The use of an infusion pump is the preferred method of administration to ensure accurate delivery of the investigational product, but gravity drips are allowed. Refer to the Investigation Product (IP) Manual for infusion rate and duration.

A cycle is defined as the time from Day 1 dose to the next Day 1 dose. If there are no treatment delays, IV administration cycles will be once every 21 days (\pm 2 days). Each patient may receive PF-06801591 until disease progression, unacceptable toxicity, withdrawal of consent, or study termination.

The dose level for Part 1 will be assigned by the sponsor.

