5.4.2. SC Administration (Parts 1 and 2)

Qualified and trained investigator site personnel will administer PF-06801591 at a fixed dose of 300 mg to patients by SC injection to the abdomen. A total volume of 6 mL must be administered subcutaneously for a dose of 300 mg of PF-06801591. Ideally, 3 subcutaneous injections of 2 mL should be administered to the abdomen, although, more injections can be done as needed, in order to have a total volume of 6 mL.

Study drug should be administered to two or more different quadrants of the abdomen (with preference given to the lower quadrants when possible); 1 or 2 injections per quadrant. The maximum number of injections per patient is 8 injections. Refer to [Appendix 9](#) for details on administration of multiple injections to the abdomen. Study staff should refer to the IP Manual for specific instructions on the handling and administration of study drug.

Similar to intravenous dosing, a cycle is defined as the time from Day 1 dose to the next Day 1 dose. Patients will receive a single dose of PF-06801591 on Day 1 of each cycle. If there are no treatment delays, a cycle will be 28 days (+/- 2 days) for SC administration. Each patient may receive PF-06801591 until disease progression, unacceptable toxicity, withdrawal of consent, patient no longer willing to participate in trial, or study termination.

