5.4.5. Dose Delays

Patients experiencing Grade 3 or 4 potentially treatment related toxicity or intolerable Grade 2 toxicity despite supportive care should have their treatment interrupted/delayed (see [Section 5.4.3](#)). Appropriate follow-up assessments should be done until adequate recovery (or until deemed irreversible) occurs as assessed by the Investigator.

Treatment resumption for patients recovering from treatment-related toxicity after 4 weeks of treatment interruption or cycle delay can be considered only if the patient is deemed to be deriving obvious clinical benefit per the investigator's best medical judgment and needs to be agreed between the investigator and the sponsor.

If a treatment interruption continues beyond Day 21 (for IV) or Day 28 (for SC) of the current cycle, then the day when treatment is restarted will be counted as Day 1 of the next cycle.

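### SAP 6.1 exposure rules can misreport dosing in descriptive tables: false IV dose reductions, a dose percentage fixed at 100% as worded, and inconsistent delay, skip and cycle-number rules

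*SAP*

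**What the plan says.** **Dose reduction.** SAP 6.1 (Treatment Administration/Compliance) defines it as "a decrease in the administered total daily dose (non-zero) compared to the planned total daily dose upon enrollment", with no tolerance. If the CRF prescribes in mg/kg but records the actual dose in mg, "the actual dose mg/kg should be calculated considering the body weight of the patient at that visit". The same bullet says reductions are not allowed unless, after discussion with the sponsor, the dose level is judged to be above the MTD.

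**Weight and IV dose.** Protocol 5.4.1 says: "The decision to recalculate PF-06801591 dose based on the weight obtained at each cycle may be in accordance with institutional practice". Recalculation becomes compulsory only under the exception that follows: "however if the patient experienced either a weight loss or gain of >10% compared to the weight used to calculate the most recent dose". The weight footnote to the Part 1 IV Schedule of Activities repeats this. The opening sentence of 5.4.1 points the other way, stating that the dose is adjusted for weight every cycle.

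**Percent of dose.** SAP 6.1 summarises cumulative dose and "percent of starting dose (compared to Day 1 dose of each cycle", by dose level and cycle. Protocol 5.4.2 states: "Patients will receive a single dose of PF-06801591 on Day 1 of each cycle". Protocol 3.1.1 likewise gives one dose per cycle in Part 1.

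**Delay and skip.** Under the SAP rule, an SC delay is a start later than 28 (+2) days after the previous Day 1, with no upper limit. The Part 2 example adds, in parentheses, that the start falls before day 56. An SC skip is a start later than 56 (+4) days. The IV limits are 21 (+2) and 42 (+4) days.

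**Cycle number.** After a skip, the SAP example says "the newly started cycle will be considered as cycle 3, and cycle 2 is considered skipped for this patient". Protocol 5.4.5 says that if an interruption runs past the end of the current cycle, "then the day when treatment is restarted will be counted as Day 1 of the next cycle".

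**The concern.** The exposure tables are where a reader learns whether patients received the planned dose. The SAP derives a reduction from a weight that the protocol does not oblige the site to use. A compliant site could then appear to have reduced doses, in a study where reductions are restricted to a special case. Those flags would enter the count of subjects with reductions, the number of cycles before first reduction and the table of reasons. The percent summary, as worded, cannot register an under-dose. Long intervals could be classified in two ways, and cycles could carry different numbers in different tables. Long intervals are foreseeable: protocol 5.4.3.1 allows up to 12 weeks after the last dose for recovery, and several entries in Appendix 8 call for a steroid taper of at least one month before treatment resumes.

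**Working it through.** The plan states no figure to reproduce; the check applies its own rules.

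**1. Weight.** Percent of planned mg/kg with mg unchanged = 100 / (1 + g), where g is the proportional weight change since the dose was calculated. Illustration: 3 mg/kg at an assumed 70 kg = 210 mg.

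| Weight change | Actual mg/kg | % of planned |
|---|---|---|
| +1% | 2.970 | 99.0 |
| +2% | 2.941 | 98.0 |
| +5% (73.5 kg) | 2.857 | 95.2 |
| +10% (77 kg) | 2.727 | 90.9 |
| -10% (63 kg) | 3.333 | 111.1 |

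The percentages are the same at every mg/kg dose level. Each gain counts as a decrease under the SAP, yet none exceeds 10%, so recalculation stays optional.

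Masking: at 63 kg, a dose cut from 210 to 189 mg (210 x 0.9) gives 189/63 = 3.0 mg/kg, exactly 100%, and no reduction is recorded.

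Patients at risk: protocol 9.3 plans 2 at 0.5 mg/kg and up to 9 at each of 1, 3 and 10 mg/kg, so 2 + 3 x 9 = 29. SC patients receive a flat 300 mg and are unaffected.

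**2. Percent of starting dose.** Read literally, this is the dose given in the cycle divided by the Day 1 dose of the same cycle. With one dose per cycle, numerator and denominator are equal:
- 300 mg given: 300/300 = 100%.
- 150 mg given: 150/150 = 100%, against 150/300 = 50% of planned.

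**3. Delay and skip, SC.** The thresholds are 28 + 2 = 30 and 56 + 4 = 60 days.

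| Day 1 to Day 1 interval | General rule | With the example's limit |
|---|---|---|
| 31-55 days | delay | delay |
| 56-60 days | delay | neither |
| over 60 days | delay and skip | skip |

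If the skip example is taken to include day 60 itself, the unclassified days are 56 to 59. For IV the SAP gives no upper limit for a delay, even by example, so there is no gap; intervals over 42 + 4 = 46 days are both delay and skip.

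**4. Cycle number.** Take an SC patient whose second dose comes more than 60 days after the first. Under protocol 5.4.5 that dose is Day 1 of the next cycle, cycle 2. Under SAP 6.1 it is cycle 3. The SAP also defines Day 1 of a cycle as the first dosing date within it, so a skipped cycle 2 has no Day 1.

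**The case against.** Much of the case against a broader claim stands.

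- **Gap at days 56 to 60.** A reader might infer that the SAP leaves these days unclassified. The general rule has no upper limit, so by the rule they are delays. The gap arises only if the example's parenthesis is treated as part of the rule. What remains is a rule and an example that disagree.
- **Trough concentrations.** A reader might infer that renumbering shifts the Part 2 troughs by cycle. SAP 5.3 assigns data to the scheduled visit as designated in the eCRF, and the trough analysis in SAP 6.3.2 does not invoke the skip rule. No endpoint effect is established.
- **Percent summary.** The wording could be meant as each cycle's Day 1 dose against the first dose, which would not be 100% by construction. Cumulative dose is summarised alongside, and a by-subject, by-cycle listing gives percentage of planned dose. Deviations therefore remain visible; only this one summary is uninformative on its literal reading.
- **Weight.** The conversion applies only when the CRF units differ, and the CRF is not available here. The opening of protocol 5.4.1 suggests adjustment every cycle, and a site that recalculates produces no artefact. The share of sites that do not is unknown. The SAP tabulates reasons for reductions, which helps, but a flag derived from weight alone corresponds to no site decision and has no natural reason to attach.
- **Frequency.** One could quote the chance that a later weight exceeds the first, 1 - 1/k over k cycles: 75% by Cycle 4 and 83% by Cycle 6. This assumes a site that never recalculates, exchangeable weights with no trend, and every patient reaching that cycle. It is a scenario, not an estimate for this trial.

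**Conclusion.** The point holds as a set of reporting defects in SAP 6.1. The firmest are the visit-weight rule, which labels compliant IV dosing of 90.9% to 99.0% of planned as a reduction, and the direct conflict with protocol 5.4.5 over cycle numbers. The percent denominator is wrong on its literal reading, and the delay rule conflicts with its example.

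The weight defect is confined to about 29 Part 1 IV patients at most under the four pre-specified dose levels. It requires a site that leaves the mg dose unchanged within the 10% tolerance and a CRF that records mg against a mg/kg prescription.

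A reader might infer that the main results are compromised, and the documents do not support that. These are descriptive exposure summaries. DLT, ORR and the analysis-set definitions do not use them, and the per-protocol limits (below 50% or above 150% of planned dose) lie far outside a 10% weight drift. Severity is minor, but the corrections are specific.

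**What to change.** Amend SAP 6.1 before the exposure tables are produced:

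1. Compute actual mg/kg with the weight used to prepare that dose. In the example, 210/70 = 3.0 mg/kg (100%) after any gain within tolerance, and the masked cut shows as 189/70 = 2.7 mg/kg (90%). If that weight is not in the database, flag a reduction only below 90% of planned mg/kg. This removes the false flags, since the worst case within tolerance is 90.9%, but it does not cure the masking after weight loss.
2. Summarise percent of dose against the planned dose at enrolment (mg/kg for IV, mg for SC).
3. As reporting classes, define SC delay as over 30 to 60 days and skip as over 60 days, and IV delay as over 23 to 46 days and skip as over 46 days. Align the example with the rule, so that every late interval falls in exactly one class.
4. Reconcile the SAP's cycle numbering with protocol 5.4.5, use one numbering in all by-cycle tables, and report a skip as a flag.

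The cost is SAP wording and programming. Doses, dosing dates and cycle weights are already collected; whether the preparation weight is held in the database or only in site preparation records needs checking.
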